2.7 DATA ANALYSIS

For both primary safety endpoints 1 and 2, pooling of data from the Corox OTW BP, Corox OTW-S BP, and Corox OTW-L BP LV leads will be justified as part of the final data analysis. The differences in outcomes for the Corox OTW BP, Corox OTW-S BP, and Corox OTW-L BP LV leads will be tested using an exact, Chi-square test. If no evidence is found of differences between the Corox OTW BP, Corox OTW-S BP, and Corox OTW-L BP LV leads ($p > 0.05$), then the results will be considered poolable for purposes of testing the protocol hypotheses associated with the two primary endpoints. If evidence of differences is found for a given endpoint, then the hypotheses for that endpoint will additionally be tested separately for each LV lead.

CELESTIAL REGISTRY PROTOCOL

Primary safety endpoint 1 will be evaluated by performing an exact, noninferiority test comparing a binomial proportion (overall SAE free-rate at 5 years) to 92.5%, with a noninferiority delta of 5%. Equivalently, the upper, one-sided 95% confidence bound for the absolute difference between the overall SAE free-rate and 92.5% must not exceed 5%.

The evaluation of primary safety endpoint 2 will be based on the exact, two-sided 95% confidence interval for the observed, individual SAE rates at 5 years. The upper bound of these 95% confidence intervals must be less than 1%.

The secondary endpoint of successful biventricular pacing will be summarized as a success rate at each of the scheduled CELESTIAL follow-up visits through 5 years post-enrollment, together with the associated exact, 95% confidence intervals.

The secondary endpoint of other SAEs at 5 years, which were excluded from the primary safety analyses (listed in Table 5), will also be summarized as SAE rates together with their associated exact, 95% confidence intervals.

The secondary endpoints of pacing threshold and impedance measurements for the Corox BP LV leads will be summarized at scheduled visits where they were evaluated, using standard measures, including means, standard deviations, medians, minimums, and maximums.

The secondary endpoint for overall incidence of serious adverse events that meet the primary endpoint 1 criteria will be evaluated separately for each Corox BP lead model using the criteria established for primary safety endpoint 1 and 2.

2.7.1 Trend Analyses

The primary safety endpoints are evaluated at 5 years post-enrollment against pre-specified performance levels (92.5% for overall freedom from Corox BP LV lead-rated SAEs, 1% for individual SAE rates). To monitor the ongoing incidence of any potential SAEs against the accumulating follow-up exposure post-enrollment, Kaplan-Meier actuarial survivor curves will be prepared at the reporting intervals for these safety outcomes. Root causes for any failures, regardless of the incidence rates, will be investigated.

If the observed cumulative survival rates fall below the 5-year target values (92.5% for overall freedom from SAEs, 99% for individual SAEs) at any time during the study, or are projected to fall below the target values, then BIOTRONIK will summarize the observed data and the results of its failure investigations, and report the findings to the FDA at or before the next scheduled status report. If at any time a single unanticipated serious adverse event or device failure, or combination of events, is believed to have implications regarding the safety of current or future patients, then this will be reported immediately to the FDA.

CELESTIAL REGISTRY PROTOCOL

2.7.2 Missing Data

The reasons for any missing data in the study will be documented. The sponsor will examine both missing-data patterns, which describe which values are observed and which are missing, and the missing-data mechanisms, which concern the relationship between missingness and the values of variables in the study data set [R.J.A. Little and D.B. Rubin, 2002, Statistical Analysis with Missing Data, 2nd edition, Wiley and Sons].

For evaluation of the primary study endpoints (safety endpoints 1 and 2), only patients who achieve 5 years of follow-up or have experienced a serious adverse event prior to 5 years will be included in the evaluation of the associated hypotheses. The secondary endpoint of other SAEs at 5 years, excluded from the primary safety analyses, will be analyzed in similar manner. There will be no imputation for these missing adverse event outcomes.

For purposes of Kaplan-Meier actuarial analyses, described in Section 2.7.1 Trend Analyses, all SAE data on enrolled patients will be included, with follow-up time censored at the time of withdrawal or last completed follow-up visit.

Secondary endpoints, which include successful biventricular pacing, pacing thresholds, sensing and impedance measurements will be analyzed in two ways. Initially, all available results will be summarized by scheduled visit through the 5 years of study follow-up. Afterwards, a last value carried forward (LVCF) will be used to estimate the values at the final 5-year follow-up evaluation.

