### 3. ANALYSIS POPULATIONS

The primary and secondary endpoints analyses will be conducted based on pre-defined populations as described below.

The primary endpoint per-protocol analysis population will be used to conduct the primary endpoints 1 and 2 analyses because these endpoints are based on SAEFR and SAE rates at 5 years post-implant respectively. The secondary endpoint per-protocol analysis population will be used to conduct the secondary endpoints 5 and 6 analyses because these endpoints examine primary endpoints 1 and 2 based on originally implanted lead models; therefore, are examined at 5 years post-implant. The intention-to-treat population will be used to conduct the secondary endpoints 1 through 4 analyses and all additional data of interest because these endpoints are continuous and examine measurements and event rates throughout the study; therefore, are not limited to only examining subjects who complete 5 year follow-up.

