#### 3.1 INTENTION-TO-TREAT (ITT) ANALYSIS POPULATION

The intention-to-treat (ITT) population includes all subjects enrolled in the study. The ITT subjects have documentation of informed consented and implant of the Corox LV study lead. This population includes all subjects enrolled in the study.

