### 5.3 SECONDARY ENDPOINTS

There are no formal hypothesis tests associated with the secondary endpoints.

#### 5.3.1 Secondary Endpoint 1

Secondary endpoint 1 examines the successful biventricular pacing in a BIOTRONIK CRT device at scheduled CELESTIAL registry follow-up visits. The mean, standard deviation, minimum, and maximum of the biventricular pacing percentage will be reported for each visit. This endpoint will be evaluated using the subject population defined in section 3.1 Intention-to-Treat (ITT) Analysis Population.

#### 5.3.2 Secondary Endpoint 2

Secondary endpoint 2 examines the rates of serious adverse events excluded from primary safety endpoint. The serious adverse event rates will be reported along with a Kaplan-Meier actuarial graph and case summary will be reported to assess this endpoint. The estimated freedom from adverse event at 5 years along with the standard error and 95% confidence intervals will also be reported. This endpoint will be evaluated using the subject population defined in section 3.1 Intention-to-Treat (ITT) Analysis Population.

#### 5.3.3 Secondary Endpoint 3

Secondary endpoint 3 examines the sensing, pacing threshold, and pacing impedance measurements for the Corox LV leads at scheduled CELESTIAL registry follow-up visits. The mean, standard deviation, median, minimum, and maximum of each measured values be reported for each visit. This endpoint will be evaluated using the subject population defined in section 3.1 Intention-to-Treat (ITT) Analysis Population.

#### 5.3.4 Secondary Endpoint 4

Secondary endpoint 4 examines the individual electrical parameters of the Corox OTW BP LV lead, the Corox OTW-S BP LV lead, and the Corox OTW-L BP LV lead. The electrical parameters presented will be the sensing, pacing threshold, and pacing impedance measurements for each lead model at scheduled CELESTIAL registry follow-up visits. The mean and standard deviation of each measured value will be

reported for each visit. This endpoint will be evaluated using the subject population defined in section 3.1 Intention-to-Treat (ITT) Analysis Population.

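### Protocol and SAP give secondary endpoint 2 (the Table 4 SAEs) different analysis sets and estimators, and the protocol's version biases the rates upward

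*Protocol*

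**What the plan says.** Protocol 2.7.2 (Missing Data) sets the rule for the two primary safety endpoints: "only patients who achieve 5 years of follow-up or have experienced a serious adverse event prior to 5 years will be included" in the hypothesis evaluation. The next sentence extends it to secondary endpoint 2: "The secondary endpoint of other SAEs at 5 years, excluded from the primary safety analyses, will be analyzed in similar manner". It then adds: "There will be no imputation for these missing adverse event outcomes". Protocol 2.7 (Data Analysis) gives the statistic: these events "will also be summarized as SAE rates together with their associated exact, 95% confidence intervals". That paragraph points to Table 5 for the list of events, but the list is in Table 4.

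The SAP takes a different route. Section 3 states: "The intention-to-treat population will be used to conduct the secondary endpoints 1 through 4 analyses", on the ground that these endpoints "are not limited to only examining subjects who complete 5 year follow-up". Section 3.1 defines the set: "The intention-to-treat (ITT) population includes all subjects enrolled in the study". Section 5.3.2 ("Secondary endpoint 2 examines the rates of serious adverse events excluded from primary safety endpoint") repeats the all-enrolled population. It asks for event rates, a Kaplan-Meier graph, and a 5-year freedom-from-event estimate with standard error and 95% confidence interval.

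Protocol 2.7.2 does use all enrolled patients, censored at exit, for Kaplan-Meier curves. It ties those curves to the trend analyses of 2.7.1, which monitor the primary safety outcomes, and not to the reported rate for secondary endpoint 2.

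**The concern.** One endpoint has two denominators and two kinds of estimate, and the available text does not say which document prevails. The SAP's stated reason for using all enrolled subjects is a reason against the protocol's rule, yet the protocol sentence stands.

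The choice affects the result in a known direction. Under the protocol rule a patient with an event always counts in both numerator and denominator, whereas an event-free patient who exits before 5 years disappears from the denominator. Some Table 4 rows are early by definition (dislodgement up to 180 days), so nearly all such events are captured before attrition has acted. For non-lead-related death, the event itself is the exit. Table 4 also prints rate ranges from prior studies beside each row. The plan does not make them a formal comparator, but they are the only reference figures a reader has for these events.

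**Working it through.** **Inputs.** Enrolment N = 2500 (Protocol 3.1). Attrition is at most 50% over 5 years, all causes including death and explant (Protocol 2.6, Study attrition; SAP 5.6). Prior rates are from Protocol Table 4. The documents do not give the timing of events or the share of event patients who complete, so these are assumptions and ranges are shown.

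**The plan's own figure.** The only stated calculation that uses this attrition is in Protocol 2.6: 1000/0.5 = 2000 and 240/0.5 = 480. Both reproduce. No rate or sample size is stated for secondary endpoint 2.

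**Step 1: protocol rate against crude all-enrolled rate.** Let e be the proportion of enrolled patients with the event and r the retention of event-free patients. Assume only the row's own event keeps a non-completer in the set.

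- Protocol rate = e / (e + r(1 − e)); crude rate = e; ratio = 1 / (e + r(1 − e)).
- With r = 0.5 and e = 5.0%: 125 / (125 + 0.5 × 2375) = 125/1312.5 = 9.5%, ratio 1.90. The exact 95% intervals are 4.2–5.9% (125/2500) and 8.0–11.2% (125/1312), which do not overlap.

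| Crude rate e | Protocol rate, r = 0.5 | Ratio |
|---|---|---|
| 0.2% | 0.4% | 2.00 |
| 1.9% | 3.7% | 1.96 |
| 3.6% | 6.9% | 1.93 |
| 9% | 16.5% | 1.83 |
| 14% | 24.6% | 1.75 |
| 36.8% | 53.8% | 1.46 |
| 48.9% | 65.7% | 1.34 |

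**Step 2: death.** No patient who dies completes, so with 1250 completers the protocol rate is deaths / (deaths + 1250). At 18.9%: 472.5/1722.5 = 27.4%, ratio 1.45. At 6.2%: 155/1405 = 11.0%, ratio 1.78.

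**Step 3: lower attrition.** For rare events the ratio tends to 1/r. If 10% per year is compounded, r = 0.9^5 = 0.59 and the ceiling is 1/0.59 = 1.69; 5.0% then reads 8.2%, and death at 18.9% reads 24.2%. With 20% attrition the ceiling is 1/0.8 = 1.25.

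**Step 4: against the SAP's Kaplan-Meier estimate.** Suppose events are rare and evenly spread, and the 50% who leave do so uniformly over 5 years. The crude all-enrolled proportion then captures 0.5 × 1 + 0.5 × 0.5 = 0.75 of the 5-year risk, and the protocol rate is about 0.75/0.5 = 1.5 times the Kaplan-Meier estimate. Simulation under these assumptions gives 1.48 at a 0.2% rate, 1.45 at 9% and 1.27 at 40%. If events cluster soon after enrolment, it gives 1.98 at 0.2%, falling to 1.43 at 40%.

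**Step 5: if any SAE keeps a patient in the denominator.** If patients who die of non-lead causes (6.2–18.9%) stay in for every row, the denominator is 1405 to 1722.5 and the ratio 2500/1405 = 1.78 to 2500/1722.5 = 1.45. Suppose non-lead hospitalisation (27.4–48.9%, assumed equally common among the other non-completers) also keeps them in. The denominator is then 1405 + 0.274 × 1095 = 1705 to 1722.5 + 0.489 × 777.5 = 2103, and the ratio about 1.5 to 1.2.

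**The case against.** The strongest objection is about size. A near two-fold gap needs four things together: attrition at the figure the protocol itself calls a maximum, a rarer event, a crude comparator, and retention of a non-completer only for the row's own event. The last is open to doubt. Protocol 2.7.2 keeps anyone with an SAE before 5 years, and Protocol 7.6 builds the primary denominator from patients with no, related or unrelated SAEs. If that carries over, the ratios are those of Step 5. This stands, so the two-fold figure is a ceiling and not an expected gap.

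A reader might also infer that ordinary rates would look clearly worse than the Table 4 ranges. That is not generally so. At 50% attrition a dislodgement rate leaves its 1.9–9% range only above 0.045/0.955 = 4.7%, and a death rate leaves 6.2–18.9% only above 0.0945/0.811 = 11.7%. Rates below those stay inside. The ranges carry no hypothesis or performance goal, and enrolment 7–180 days after a successful implant selects the early-event rows under either population.

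Nor do the documents support reading the crude all-enrolled rate as the correct one. It treats dropouts as event-free and undercounts late events (Step 4), so the two crude rates err in opposite directions.

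Finally, the SAP already chooses all enrolled subjects and says why. That makes the remedy easier, but it does not settle which document governs.

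**Conclusion.** The contradiction is real and visible in the text: two populations and two estimators for one endpoint, with no order of precedence. The direction of the protocol's bias is upward. Its size depends on assumptions the documents do not settle. At 50% attrition with row-specific retention, the protocol rate is at most about 1.8 to 2.0 times the crude all-enrolled rate for events up to 9%. It is about 1.3 to 1.5 times for the commonest events and for death at the top of its range, although death at the bottom of its range reaches 1.78. Against Kaplan-Meier it is about 1.3 to 1.5 times for evenly spread events, and more if they cluster early. The ratio is smaller at lower attrition, or if any SAE keeps a patient in. The endpoint is descriptive, so no hypothesis test is affected. The matter should still be reconciled, because the reported safety rates and their intervals depend on it.

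**What to change.** - In Protocol 2.7.2, delete the sentence that extends the completers-plus-events rule to secondary endpoint 2.
- In Protocol 2.7, replace the proportion with exact interval for this endpoint with the SAP's all-enrolled, time-to-event 5-year estimate and 95% confidence interval as the main result, every patient contributing follow-up until exit. Deleting the 2.7.2 sentence alone would leave an exact binomial interval that does not fit censored follow-up. Correct the Table 5 reference to Table 4 in the same edit.
- In both documents, label any crude rate as descriptive.
- For the non-fatal rows, treat death as a competing event and report cumulative incidence.
- State the same population and estimator in Protocol 2.7 and SAP 3 and 5.3.2.

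The cost is a small edit to the protocol and the SAP, with whatever approval the FDA-required registry needs for a protocol change. No new data or patients are needed.

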For the sample size calculation, a maximum loss to follow-up of 10% per year (50% over 5 years) was assumed. The loss to follow-up rate encompasses all causes for subjects to be exited from the study, including subject death, device explants, patient directed withdrawals, physician directed withdrawals, and loss of contact with the subject. BIOTRONIK will make every effort to limit the loss to follow-up, for reasons other than subject death and device explants unrelated to device design or performance, to less than 20% of the total registry enrollment cohort.

Minimum cohort size

The pre-specified secondary analysis will be conducted as an ad hoc analysis, meaning no testable hypothesis is being stated. Therefore, the minimal cohort size to analyze each lead model is based on an assumption of an equal 1/3 distribution of each lead model being enrolled in the CELESTIAL Registry. For the evaluation of the Corox OTW-L BP lead, a minimum of 600 evaluable subjects will be necessary.

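### Protocol 2.7.2 adds a carried-forward 5-year estimate of pacing and lead measurements with no stop at death or explant, and the SAP does not mention it

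*Protocol*

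**What the plan says.** Protocol 2.7.2 states: "Secondary endpoints, which include successful biventricular pacing, pacing thresholds, sensing and impedance measurements will be analyzed in two ways". The first way uses the data as collected: "Initially, all available results will be summarized by scheduled visit through the 5 years of study follow-up". The second is imputation: "a last value carried forward (LVCF) will be used to estimate the values at the final 5-year follow-up evaluation". The section does not say whose values may be carried, for how long, or what happens at death or explant. For serious adverse events the same section does the opposite: it rules out imputation and censors the Kaplan-Meier follow-up at withdrawal or last visit.

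Protocol 2.6 sets the scale of the missing data: "a maximum loss to follow-up of 10% per year (50% over 5 years) was assumed". It defines the loss broadly: "The loss to follow-up rate encompasses all causes for subjects to be exited from the study, including subject death, device explants", together with withdrawals and lost contact.

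The SAP handles these endpoints in 5.3.1, 5.3.3 and 5.3.4 with per-visit descriptive statistics in all enrolled subjects. For pacing: "The mean, standard deviation, minimum, and maximum of the biventricular pacing percentage will be reported for each visit". Carrying values forward appears nowhere in the SAP, which has no missing-data section.

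**The concern.** A carried-forward value stands in for a measurement at 5 years. For a patient who left the registry but still has the lead, it assumes nothing changed after the last visit. For a patient who died, or whose lead was removed, there is no 5-year measurement to estimate. The rule as written does not separate these cases.

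The summary's purpose statement includes confirming successful biventricular pacing, and Protocol 2 describes a secondary effectiveness endpoint of long-term pacing delivery through 5 years. A 5-year figure that mixes 5-year measurements with values from years earlier does not describe 5-year performance. For pacing there is a plausible direction. Protocol 3.2.4 says that patients without effective CRT should not be enrolled, so early values are selected to be good, and carrying them forward favours the lead if pacing later declines. For threshold, sensing and impedance, the direction depends on a drift that the documents do not give.

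Because the SAP is silent, a reader also cannot tell whether this analysis will appear in the final report.

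**Working it through.** **Who would be filled in.** Set the two protocol sections side by side. Section 2.7.2 carries the last value to the final evaluation without restriction. Section 2.6 counts as lost those who leave for any reason, "including subject death, device explants, patient directed withdrawals, physician directed withdrawals, and loss of contact with the subject". Nothing in either section takes deaths or explants out of the carried-forward set. Section 2.6 speaks of device explants without separating lead from generator, so the no-lead case applies where the lead was removed. A patient with no prior value could not be filled in.

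**How many.** Inputs: minimum enrollment 2500 (Protocol 3.1); loss 10% per year, 50% over 5 years (Protocol 2.6).

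- The plan's own inflation reproduces: 240/(1 − 0.5) = 480 and 1000/(1 − 0.5) = 2000.
- At 50%: 2500 × 0.50 = 1250 values carried at most, 1250 observed.
- If 10% per year compounds: 1 − 0.9^5 = 0.4095, so 2500 × 0.4095 ≈ 1024 carried, 1476 observed.

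The aim in Protocol 2.6 to hold some losses "to less than 20% of the total registry enrollment cohort" leaves out deaths and explants unrelated to device design or performance, so it is not a total.

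**For how long.** Assume a constant exit hazard λ over T = 5 years and total attrition d = 1 − exp(−λT). The mean exit time among leavers is 1/λ − T(1 − d)/d.

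- d = 0.50: λ = ln 2/5 = 0.1386; 7.21 − 5 × 0.5/0.5 = 2.21 years, so values are carried 5 − 2.21 = 2.79 years on average.
- d = 0.4095: λ = −ln 0.9 = 0.1054; 9.49 − 5 × 0.5905/0.4095 = 2.28 years, carried 2.72 years.

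This treats the last value as measured at exit. A last visit before exit lengthens the carry slightly.

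**Effect on the estimate.** Assume also that pacing success falls linearly by F points over 5 years, and that leavers follow the same course as stayers. Each carried value is then too high by F × (years carried)/5, and the bias in the mean is d × F × (years carried)/5.

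- d = 0.50: 0.50 × 2.79/5 = 0.28, so bias = 0.28F.
- d = 0.4095: 0.4095 × 2.72/5 = 0.22, so bias = 0.22F.

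| Assumed fall F | Bias at 50% loss | Bias at 41% loss |
|---|---|---|
| 8 points | 2.2 points | 1.8 points |
| 2 points | 0.6 points | 0.4 points |
| 0 | 0 | 0 |

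For example, a fall from 98% to 90% at 50% loss gives 0.5 × 90 + 0.5 × (98 − 8 × 2.21/5) = 92.2% instead of 90%. The falls are assumptions. The documents give no long-term drift: Protocol Table 2 covers threshold and impedance only and stops at six months, with 15 tests. The reference value here is what would be seen had everyone stayed under observation, which has no meaning for patients who died. The arithmetic sizes the drift problem; it does not rescue the estimate for those patients.

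**Protocol against SAP.** Protocol 2.7.2 requires two analyses of these measures. SAP 5.3.1, 5.3.3 and 5.3.4 describe one, by visit, and do not say that the other has been dropped.

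**The case against.** The strongest reply is that little rests on this analysis. The observed by-visit summaries come first, and Protocol 2.7 gives pacing success at each visit an exact 95% confidence interval without imputation, so an unfilled 5-year figure would stand beside the carried-forward one. The endpoints are secondary, the SAP states no formal hypotheses for them, and if the SAP is followed no carried-forward result is produced. Protocol 2.7.2 also commits the sponsor to record reasons for missing data and to examine patterns and mechanisms. All of this stands and limits the weight of the point. It does not settle which document governs, and the imputation is fixed whatever that examination shows.

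Several stronger readings are tempting but not supported:

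- That half the cohort will be filled in. The 50% is a planning maximum; compounding gives 41%, and actual attrition is not in the documents.
- That the 5-year interval will be falsely narrow. Counting 2500 values instead of 1250 would shrink a standard error by 1 − √(1250/2500) = 29% (23% at 41% loss), but no interval is specified for the carried-forward values.
- That the carried value is usually the last good one before lead trouble. Protocol 3.2.5 requires lead parameters at each follow-up, routine or unscheduled, so a failing value may be the last one recorded.
- That lead failures would be hidden. Lead-related serious adverse events within primary endpoint 1 are counted there, and missing adverse event outcomes are not imputed.
- That the protocol states that dead or explanted patients are filled in. This is an inference from 2.6 and 2.7.2 together; neither section says it, and neither prevents it.

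**Conclusion.** The point holds in limited form. As written, Protocol 2.7.2 yields 5-year lead values for patients with no lead or no life at 5 years. It also biases the carried-forward estimate toward earlier values whenever performance drifts. Under a constant exit hazard and a linear fall shared by leavers and stayers, the bias is 0.22 to 0.28 of the fall for 41% to 50% attrition, and zero if nothing changes. The size of any fall is assumed. The firmest part needs no assumption: the protocol requires the analysis and the SAP omits it.

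A reader might infer that the registry's 5-year pacing result, or its safety conclusions, are compromised. They are not: the observed by-visit results remain, and neither primary endpoint uses carried-forward values. The change is still worth making before the final analysis, because it removes a hard-to-interpret estimate at almost no cost.

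**What to change.** Delete the carried-forward sentence from Protocol 2.7.2 so that it agrees with SAP 5.3.1, 5.3.3 and 5.3.4. In both documents, report the observed values at each visit with two counts beside them: patients still alive with the lead in service, and patients measured.

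If the analysis is kept, name it a sensitivity analysis in both documents, do not carry values past death or lead explant, and report how many values are carried and for how long.

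A repeated-measures model for the 5-year value is optional. It would use all visits, but even with records ended at death or explant it still estimates a mean as if those patients had continued, so it does not by itself resolve the problem of deaths.

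The cost is a few sentences in each document, with no new data collection. The downside is that the 5-year summary rests on fewer patients (about 1250 to 1476 of 2500 under the planning assumptions) and is less precise.
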